**4.5 HANDLING OF WITHDRAWALS**

If a patient is withdrawn from the study or fails to return either at his or her request or at the investigator's discretion after randomization, every effort should be made to determine the reason. This information will be recorded on the patient's electronic case report form (eCRF). All patients who withdraw from the study prematurely, regardless of cause, should undergo all early termination assessments (see Section 5.5). It is vital to obtain follow-up data for any patient withdrawn due to an AE or abnormal laboratory test finding. In any case, every effort must be

made to undertake safety follow-up procedures. If a patient wishes to withdraw, the difference between treatment discontinuation and study withdrawal will be explained. Patients should be encouraged to continue the follow up visits and at minimum provide a Ht measurement at 12 months of the initial treatment period even if they discontinue the study treatment early.

#### 4.6 SPONSOR'S TERMINATION OF STUDY

The Sponsor reserves the right to discontinue the study at any time for any reason.

Regulatory Authorities also have the right to terminate the study.

### 5. INVESTIGATIONAL PLAN AND STUDY PROCEDURES

A schedule of events for this study is shown in [Appendix A](#). No protocol related procedures, including the cessation of prohibited concomitant medications should be performed before patients provide writtena assent (where applicable) and consent from the parent(s) or legal guardian(s) is obtained. Study related events and activities including specific instructions, procedures, concomitant medications, dispensing of study drugs and descriptions of AEs should be recorded in the appropriate source documents and/or eCRF.

#### 5.1 VISIT 1 - SCREENING PERIOD (DAY – 56 TO DAY -1)

The screening period will last up to 8 wksb and can be conducted over several visits prior to randomization, to minimize blood volume withdrawals per visit. Screening visits are intended to collect current clinical data and to perform all required investigations needed to establish a patient's eligibility for the study. Prior to any study specific assessments, written assent from pediatric patients (where applicable based on age and country) and consent from the parent(s) or legal guardian(s) will be obtained. Upon completion of the Informed Consent process and obtaining written consent from the parent(s) or legal guardians(s) a patient is deemed to be 'enrolled into the study'.

The following assessments will be conducted at these screening visits:

- Inclusion/exclusion verification.
- Parental Htc, and patients' Ht, Ht SDS, HV and HV SDS.
- Body weight and BMI SDS.
- Medical history, including a description of pituitary deficiencies, concomitant and previous medications.
- Overall health status assessment, including complete physical examination and vital signs.
- Pubertal status (according to Tanner stages).

a Illiterate patients should provide their consent in a method that is accepted according to local regulations.

b If the patient's screening process is delayed because of a benign illness or unforeseen benign condition (i.e. pharyngitis, viral GI problems, minor accident or trauma, etc.) or other technical issue that is related screening procedures (for example, delays with laboratory results) extra time will be added to the duration of the screening period, but not in excess of an additional four wks (total of 12 wks screening period).

c It's recommended that parents will be measured at the site. If measured parental Ht is not available an estimate should be provided by the parent. It should also be noted that the patient's birth date is required for accurately reporting of Ht SDS.

Effective Date: Date of final electronic approval

- BAa determination with the method of Greulich-Pyle using a central BA reader.
- Assessment of biochemical markers and stimulation tests:
  - Two (2) different GH stimulation (provocation) tests from the following list: ITT (with serum cortisol response to hypoglycemia if insulin stimulation test is chosen); arginine test; clonidine test; glucagon test; L-dopa test. The minimal duration and number of samples must conform to the specifications in [Appendix B](#) for each test.

The use of a local laboratory for assessment of GH serum levels (and glucose and serum cortisol if the insulin tolerance test is performed) might be acceptable, if done prior to ICF signature, and if the results are reviewed and approved by the global study MM **prior to study entry**.

- Assessment of morning cortisol (at 8 am ± 1 hour).  
If morning cortisol is below 190 nmol/L (7 µg/dL), test for adrenal insufficiency will be required – Low dose ACTH or CRH stimulation test (only if the patient was not previously assessed for the hypothalamus-pituitary-adrenal axisb or has been diagnosed with adrenal insufficiency).
- Assessment of biochemical markers: IGF-1, IGF-1 SDS, IGFBP-3 and IGFBP-3 SDS serum levels.
- Assessment of anti-hGH Ab.
- Safety laboratory tests: chemistry, hematology, urinalysis.
- Assessment of thyroid function: TSH, FT4.
- Parameters of glucose metabolism: overnight fasting insulin, overnight fasting glucose and HbA1C.
- Head MRIc, if possible with contrast or CT scan – recommended to be performed only after the two GH stimulation tests.
- Assessment of karyotype in girlsd.
- SHOX gene evaluatione.

The Global Study MM will review key data and all test results obtained during Screening; the eligibility will be confirmed by the Global Study MM **prior to randomization** of each patient.

It is recommended that the Investigator randomize the patient within 7 days of Global Study MM confirmation of eligibility and to bring the patient back in for the Baseline visit (Visit 2) within 2 wks of randomization.

a Historical BA assessment might be accepted if they were done with the method of Greulich-Pyle no more than 6 months prior to the ICF signature date. If the patient is eligible, the BA should be repeated at Visit 2 prior to dosing. The Visit 2 scan will be the Baseline scan for these patients.

b ITT with serum cortisol response to hypoglycemia is adequate for assessment of adrenal insufficiency and no ACTH stimulation test is required if such results are available.

c Historical MRI or CT is permitted if within 12 months; MRI or CT which was conducted no more than 12 months prior to ICF signature data will be acceptable. For GHD associated with a congenital CNS defect, the medical monitor could allow for use of the historic MRI or CT > 12 months old.

d Historical karyotype data and chromosomal microarray data are acceptable.

e Historical data is acceptable. SHOX gene evaluation is only necessary for isolated GHD with a normal brain MRI. Patients with clear multiple pituitary hormone deficiencies or structurally abnormal pituitary gland do not require SHOX gene evaluation.

## 5.2 MAIN STUDY TREATMENT PERIOD (DAY 1/BASELINE TO MONTH 12)

Eligible patients will be randomized (central randomization within each regiona) in a 1:1 fashion within each stratum to receive either weekly MOD-4023 (0.66 mg/kg/wk) or daily Genotropin® (0.034 mg/kg/day or 0.24 mg/kg/wk) for 12 months.

Visit 2 (Day 1/Baseline) will be conducted on day of first dosing. Subsequent visits, Visit 4 (Month 1/Wk 4 [+1 wk]), Visit 5 (Month 3/Wk 13 [ $\pm 1$  wk]), Visit 6 (Month 6/Wk 26 [ $\pm 1$  wk]), Visit 7 (Month 9/Wk 39 [ $\pm 1$  wk]), and Visit 8 (Month 12/Wk 52 [ $\pm 1$  wk]) will be conducted on day 4 (-1 day) post doseb to obtain IGF-1 measurements expected to reflect average levels throughout the wk.

Visit 3 (Day 10 [+4 days]c post first dose) for the collection of immunogenicity and PK sample will be conducted for MOD-4023 arm only. This visit can be done at the patient's home or at the study site, based on local regulations and nurse availability. If home visit is conducted, a questionnaire, as described in [Appendix I](#) should be completed, collecting information on AE, local tolerability and concomitant medications.

Visits 6a (Month 6/Wk 26 [ $\pm 3$  wk]) and Visit 8a (Month 12/Wk 52 [ $\pm 1$  wk]) will be conducted on dosing day for the MOD-4023 arm only for the collection of immunogenicity and PK sample. This visit can be done at the patient's home or at the study site, based on local regulations and nurse availability. If home visit is conducted, a questionnaire as described in [Appendix I](#) should be completed as well. Samples must be collected prior to dosing of MOD-4023.

In parallel to MOD-4023 patients Visit 3 (Day 10 [+4 days]), a phone interview will be conducted to Genotropin® arm patients and/or parents/guardians according to the questionnaire provided in [Appendix I](#) in which AE, local tolerability and concomitant medication information will be collected.

For the ECG that will be conducted at Visit 6b (Month 6/Wk 26 [ $\pm 3$  wks]) at 7-12 hours post-dose for MOD-4023 treated patients, patients will be requested to inject MOD-4023 during the day/night at their convenience and come to the study site at the requested time point for ECG.

Visits 6a and 6b might be combined on the same day (only if 6a is done prior to dosing).

The patient will come to the study site in the morning, perform the blood tests, afterwards will inject on site and will come back 7-12 hours post dosing for ECG assessment.

Genotropin® patients will have an ECG assessment at Visit 6 (no time limitation).

### 5.2.1 Visit 2 (Day 1/Baseline) – recommended injection days as indicated in [Appendix E](#)

Visit 2 must be conducted within 2 wks of randomization.

The following assessments will be conducted on Day 1/Baseline:

a 1. Western Europe, Israel, Australia, New Zealand, Canada and USA; 2. Central and Eastern Europe, Greece, Turkey, Latin America and Asia except for India and Vietnam 3. India and Vietnam.

b All visits, except Visit 3, can be conducted within the specified window to accommodate patient availability, but must be conducted on day 4 (-1) post dose.

c Applicable only for MOD-4023, Visit 3 assessments, if conducted on Day 14 (dosing day), should be done prior to dosing.

Effective Date: Date of final electronic approval

- Auxology measurements: Actual Ht (mean of three consecutive measurements) measured on a calibrated wall mounted stadiometer.
- AEs, local tolerability (aligned with Appendix H), and concomitant medications.
- Overall health status assessment, including complete physical examination and vital signs.
- Safety laboratory tests: chemistry, hematology and urinalysis.
- Pubertal status (according to Tanner stages).
- Assessment of thyroid function and biochemical markers: TSH, FT4, IGF-1, IGF-1 SDS, IGFBP-3 and IGFBP-3 SDS serum levels.
- Assessment of MOD-4023 serum levels (applicable for MOD-4023 arm only).
- Parameters of glucose metabolism: overnight fasting glucose, overnight fasting insulin, HbA1c.
- Parameters of lipid metabolism: overnight fasting cholesterol, triglycerides, HDL, LDL, Lp(a), FFA.
- Assessment of anti-MOD 4023 and anti-hGH Ab (depending on arm of study).
- BAa.
- ECG pre-dosing.
- Training for patients, parents or legal guardians on drug administration.
- Fundoscopy (if there are signs or symptoms indicative of benign intracranial hypertension).
- Training for patients, parents or caregiver for completing the PAT assessment.
- Administration of study drug at the study site by patient or parent/caregiver.
- MOD-4023 on-site OAT assessment (USA only).
- MOD-4023 on-site PAT assessment (USA only).
- QoL Questionnaire completion (in specific countries as indicated in [Appendix L](#)).
- Drug dispensing and accountability.

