
Effective Date: Date of final electronic approval

Baseline will be characterized with descriptive statistics (mean, SD, and 95% CI) for each treatment group.

**Primary Efficacy Sensitivity Analysis:** The ANCOVA-based primary efficacy analysis will be repeated using the modified intent-to-treat (mITT) set and the per protocol (PP) set.

The ANCOVA-based primary efficacy analysis will be repeated on the full analysis set using last observation carried forward (LOCF) in place of multiple imputation for the handling of missing data.

OAT and PAT (USA Only)

OAT and PAT results will be summarized by using descriptive statistics.

Proportion and counts of successful single injections out of total number of single injections using the MOD-4023 PEN in USA patients at Wks 1, 2, 3, 4, 5, and 6, based on the PAT will be reported. Similarly, counts and proportion of successful single injections out of total number of single injections using the MOD-4023 PEN in USA patients at Wk 1, based on the OAT will be reported. Details on the criteria constituting a successful single injection based on OAT and PAT, along with statistical methods to be used for descriptive summaries will be included in the SAP.

Comments on the PAT and OAT related to successful or unsuccessful injection attempts

The written comments provided on the PAT and OAT for successful or unsuccessful injection attempts will be listed. Any other written comments will also be listed.

Information gained by inspection of returned devices

Summary of the information gathered by inspecting the returned devices will be reported.

The QoLISSY core total score at Baseline, 12 months and change from Baseline to month 12, for each group will be summarized using descriptive statistics. This will be done for specific countries as listed in the [Appendix L](#).

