**3. STUDY DESIGN**

The study will consist of 12 months, open-label, multi-center, randomized, active controlled, parallel group study comparing efficacy and safety of weekly MOD-4023 to daily GH, Genotropin®.

Both drugs will be injected using a PEN device.

The study will be divided into two parts:

**Main Study Period (main study):** After an 8 wk screening perioda, patients meeting the eligibility criteria, as approved by global study MM, will be randomized in a 1:1 ratio to weekly SC doses of MOD-4023 (investigational treatment) or daily SC administration of Genotropin® (reference therapy) for 12 months. The key safety data will be reviewed by an independent DSMB every 4 months or on an *ad hoc* basis.

**LT-OLE Period (LT-OLE):** Patients who received MOD-4023 during the main study will continue in the LT-OLE with the same dose (mg/kg/wk) of MOD-4023. Patients who received Genotropin® during the main study will be switched to MOD-4023 and will begin treatment with a dose of 0.66 mg/kg/wk beginning no less than one day after cessation of Genotropin® treatment. The key safety data will be reviewed by an independent DSMB approximately every 6 months.

During the entire study (main study and LT-OLE), the dose of MOD-4023 and Genotropin® will be adjusted every 3 months based on the patient's body weight. Doses may be decreased for safety reasons according to the pre-defined dose-adjustment criteria (which will be based on the severity

a If the patient's screening process is delayed because of a benign illness or unforeseen benign condition (i.e. pharyngitis, viral GI problems, minor accident or trauma, etc.) or other technical issue that is related screening procedures (for example, delays with laboratory results) extra time will be added to the duration of the screening period, but not in excess of an additional four wks (total of 12 wks screening period).

of AEs or repeated, elevated levels of IGF-1). The dose will be decreased based on two, repeated day 4(-1) post-dose levels of IGF-1 SDS  $\geq +2.0$  (Section 6.4). During the LT-OLE, dose reduction for IGF-1 level  $>+2.0$  SDS will be made following consultation with the Global Study MM on an individual patient basis

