### **5.11 QoL QUESTIONNAIRE**

QoL will be measured using the QoLISSY questionnaire which was developed to provide clinicians and researchers a validated tool to assess the impact of short stature on children. The QoLISSY core questionnaire consists of 22 like-scaled items assigned to the core dimensions: Physical, Social, and Emotional.

For patients below the age of 7 and 0 days a parental QoLISSY core questionnaire will be completed guided by the parent or caregiver. Patients above and including the age of 7 and 0 days will be encouraged to complete the child QoLISSY core questionnaire on its own. Both questionnaires are provided in [Appendix L](#) as well as a designated list of countries in which it will be completed.

The QoLISSY core total score is calculated by the sum of the means of these 3 dimensions and divided by 3. All scores will be transformed from raw scores to 0 to 100 scores, consistent with the QoLISSY scoring manual. Higher values represent a higher QoL.

The QoLISSY will be administered at Visit 2 and at the end of the study Visit 8, i.e., after 12 months of treatment at designated countries (determined by availability of translated tools) per the list in [Appendix L](#).

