## 6.6 BLINDING

In order to minimize any potential sources of bias in this open-label study, certain identified roles will remain blinded to the treatment assignments (and to any other treatment-identifying information), during the main study. Details on the blinding procedures used will be provided in the Data Management Plan (DMP).

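### The only baseline QoLISSY is completed after open-label randomization, with no requirement that it precede knowledge of the arm, training or the first injection

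*Protocol*

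**What the plan says.** **Masking.** Protocol Section 3 states: "The study will consist of 12 months, open-label, multi-center, randomized, active controlled, parallel group study". Section 6.6 limits blinding to staff functions that it does not name: "certain identified roles will remain blinded to the treatment assignments", with details left to the Data Management Plan. Nothing masks the child or the parents.

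**Order of events.** Randomization follows confirmation of eligibility. Section 5.1 then asks the site to "bring the patient back in for the Baseline visit (Visit 2) within 2 wks of randomization", and Section 5.2.1 makes the limit firm: "Visit 2 must be conducted within 2 wks of randomization". Section 5.2 adds: "Visit 2 (Day 1/Baseline) will be conducted on day of first dosing".

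**Questionnaire.** Section 5.11: "The QoLISSY will be administered at Visit 2 and at the end of the study Visit 8". Appendix L and the schedule in Appendix A agree, and neither shows a QoLISSY at screening. The Visit 2 list in Section 5.2.1 includes an item beginning "QoL Questionnaire completion (in specific countries as indicated in" Appendix L, with no timing condition.

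**Analysis.** The statistical part of the synopsis plans a descriptive summary of the core total score at Baseline, at 12 months, and as "change from Baseline to month 12, for each group will be summarized". Section 8.6.4 describes only the scoring. The supplied SAP covers the long-term extension and has no QoLISSY rule.

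**The concern.** A baseline should be a value that treatment assignment cannot have influenced. A self-reported or parent-reported score collected after an open-label allocation lacks that protection. A family that has just learned it will inject weekly, or daily, may answer questions about feelings differently before the drug has had any effect.

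The protocol names the effect of each treatment on quality of life as one of its other objectives and plans to describe change from Baseline by group. If knowledge of the arm moves the baseline in one arm, that shift enters the arm's change score with the opposite sign. No earlier score exists from which a clean change could be rebuilt.

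**Working it through.** The plan gives no sample size, standard deviation or meaningful difference for QoLISSY, so it has no figure of its own to reproduce. Its only sizing, 100 per group in Section 8.1, concerns height velocity. The check is therefore mainly one of timing.

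**1. Is the baseline post-allocation?** Randomization precedes Visit 2 by 0 to 14 days (Sections 5.1 and 5.2.1), and QoLISSY is given at Visits 2 and 8 only. Every baseline score is therefore collected after randomization.

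**2. Does the family know the arm by then?** The protocol does not say when families are told. Visit 2, however, includes blood sampling for drug levels in one arm only, antibody tests that depend on the arm, training on drug administration and an on-site injection. The arm is known during Visit 2 at the latest and may be known from the day of randomization.

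**3. Is there a pre-dose condition?**

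| Visit 2 assessment | Condition | Source |
|---|---|---|
| ECG | Before dosing | Section 5.2.1 |
| Bone age, when repeated | Before dosing | Section 5.2.1 footnote; Appendix A |
| QoLISSY | None | Synopsis; Sections 5.2.1 and 5.11; Appendices A and L |

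The two objective measures are protected and the reported outcome is not.

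**4. Recall period.** Both forms in Appendix L ask about the preceding week. With a gap of g days from randomization to Visit 2, the share of the recall week that falls after randomization is min(g, 7)/7:
- g = 3: 3/7, or 43%
- g = 7: 7/7, or 100%
- g = 14: 100%

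With a gap of a week or more, the whole recall period is post-randomization.

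**5. Effect on the change score.** Let b be the difference between arms (MOD-4023 minus Genotropin) in mean Visit 2 score caused by knowing the arm. Then

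change difference = (Month 12 difference) - (baseline difference),

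so b in the baseline moves the change difference by -b. For assumed values b = 1, 3 and 5 on the 0 to 100 scale, the movement is -1, -3 and -5 points. These values are illustrations; the documents support no figure. The Month 12 difference contains no baseline term, so the baseline shift does not enter it.

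**6. Reach.** Children in the 14 countries listed in Appendix L.

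**The case against.** **Position in the Visit 2 list.** A reader might infer that the questionnaire is scheduled after the injection, because it appears below training and drug administration. The documents do not support that. The list is not stated to be chronological and does not read as such: adverse events and local tolerability are its second item, and dispensing is its last, after on-site administration. The order shows only that completion after the injection is permitted.

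**Loss of the comparison.** A reader might also infer that the quality-of-life comparison is spoiled beyond repair. It is not. Month 12 scores by group are summarized in their own right and do not use the baseline. The plan specifies no between-arm difference, model or test for QoLISSY, so the -b shift applies to a subtraction the reader would make, not to a planned result.

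**Mechanism.** The items concern reaching things, being teased, and feeling small or unhappy about height. None asks about injections. This stands, and it suggests a small shift. Some items are emotional, so an influence is plausible but not shown.

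**Persistence.** If knowing the arm moved answers equally at Visits 2 and 8, the shift would cancel in the change score, and a pre-randomization baseline would leave it in. That is true as arithmetic but does not rescue the Visit 2 baseline. A baseline taken before randomization has no expected difference between arms, so the comparison of change then agrees in expectation with the Month 12 comparison by randomized arm. The Visit 2 baseline does not secure this. Neither choice alters the fact that Month 12 answers also come from families who know the arm.

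**Other documents.** The main-study SAP and the Data Management Plan were not available and may say more about handling. They could not supply a pre-randomization score that the schedule does not collect. A stray pre-dose label above the example in the parent form is not a timing instruction, is absent from the child form, and would not address completion after randomization.

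**Conclusion.** The point holds as a low-severity design weakness. The baseline QoLISSY is a post-allocation measure in an open-label trial and has no required place relative to disclosure of the arm, training or the first dose. The descriptive change from Baseline by group can therefore carry an effect of knowing the arm. The documents do not show that it does.

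The size is unknown and probably small. The range of 1 to 5 points used above is an assumption. Exposure is confined to the Baseline and change columns of a descriptive endpoint outside the primary and secondary sets, in selected countries. Month 12 scores by arm and the height-velocity analysis are unaffected.

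The conclusion rests on two things: that families know the arm by the time they complete the form, which the plan allows but does not state, and that no unseen study document sets an earlier completion time.

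**What to change.** **Preferred.** In Sections 5.1, 5.2.1 and 5.11 and Appendices A and L, with the matching synopsis line, have QoLISSY completed at an existing screening visit before randomization. Section 5.1 already lets screening run over several visits, so no extra visit is needed. Choose a late screening visit where possible, and record the date and time of completion.

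**If it stays at Visit 2.** Make it the first procedure, before training and injection and, where possible, before the family is told the arm. Record the time. This is weaker: it does not help families who already know the arm, and the recall week may still lie after randomization.

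**Cost.** The questionnaire and the number of completions per randomized child are unchanged. With the preferred option, some children will complete the form and then fail screening. The score may also precede the first dose by several weeks. At the extreme, with completion on the first day of screening, that is 8 + 2 = 10 weeks, or 12 + 2 = 14 weeks if screening is extended, not counting any days between the end of screening and randomization. A late screening visit keeps the gap small against a 12-month change. That part of the gap lies before randomization in both arms, so it should not favor either.
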